# APPENDIX Q. PUBLICATION POLICY

All unpublished information given to the investigator by the sponsor shall not be published or disclosed to a third party without the prior written consent of the sponsor.

The results of this study may be published or presented at scientific meetings. If this is foreseen, the investigator agrees to submit all manuscripts or abstracts to the sponsor before submission. This allows the sponsor to protect proprietary information and to provide comments.

The sponsor will comply with the requirements for publication of study results:

"Recommendations for the Conduct, Reporting, Editing, and Publication of Scholarly Work in Medical Journals" (www.ICMJE.org). Publication of the results will occur in a timely manner according to applicable regulations. In accordance with standard editorial and ethical practice, the sponsor will generally support publication of multicenter studies only in their entirety and not as individual investigational center data. In this case, a coordinating investigator will be designated by mutual agreement.

Authorship will be determined by mutual agreement and in line with International Committee of Medical Journal Editors authorship requirements:

- substantial contributions to the conception or design of the work; or the acquisition, analysis, or interpretation of data for the work
- drafting the work or revising it critically for important intellectual content
- final approval of the version to be published
- agreement to be accountable for all aspects of the work in ensuring that questions related to the accuracy or integrity of any part of the work are appropriately investigated and resolved

The publications committee established by the sponsor will oversee this process. Additional publications may follow. Policies regarding the publication of the study results are defined in the financial agreement.

No patent applications based on the results of the study may be made by the investigator nor may assistance be given to any third party to make such an application without the written authorization of the sponsor.

**LIST OF ABBREVIATIONS AND DEFINITIONS OF TERMS**

Abbreviation	Term
ADA	antidrug antibodies
ANCOVA	analysis of covariance
β-HCG	beta-human chorionic gonadotropin
CMH	Cochran-Mantel-Haenszel
CNS	central nervous system
CRF	case report form
CV	coefficient of variation
e-diary	electronic diary
ECG	electrocardiogram/electrocardiography
eC-SSRS	electronic Columbia Suicide Severity Rating Scale
EOS	end of study
EOT	end of treatment
EODBT	end of double-blind treatment
ET	early termination
DB	Double-blind
FAS	full analysis set
GCS	Glasgow coma scale
HIT-6	6-item Headache Impact Test
IMP	investigational medicinal product
IRT	interactive response technology
ITT	intent-to-treat
LS	least square
MCS	Mental Health Composite Scores
MedDRA	Medical Dictionary for Regulatory Activities
NSAID	non-steroidal anti-inflammatory drug
OL-ITT	Open-label intent-to-treat
PCS	Physical Composite Scores
PDAESI	protocol-defined adverse events of special interest
PGIC	Global Impression of Change
PP	per-protocol
PTH	posttraumatic headache

Abbreviation	Term
R&D	Research and Development
MMRM	mixed model for repeated measures
SAC	Standardized Assessment of Concussion
SAP	statistical analysis plan
sc	subcutaneous(ly)
SCAT-3	Sport Concussion Assessment Tool 3rd edition
SD	standard deviation
SE	standard error
SF-12	12-Item Short-Form Health Survey
SI	standard international
SOC	system organ class
SOP	standard operating procedure
ULN	upper limit of normal
UN	unstructured covariance
WHO Drug	World Health Organization Drug Dictionary

## INTRODUCTION

This Statistical Analysis Plan describes the planned analysis and reporting for Teva Branded Pharmaceutical Products R&D, Inc. study TV48125-CNS-20024, [a phase 2, multicenter, randomized, proof-of-concept, double-blind, placebo-controlled, parallel-group study, including an open-label period, evaluating the efficacy and safety of 1 subcutaneous dose regimen of fremanezumab for the treatment of posttraumatic headache (PTH)], and was written in accordance with GSD\_SOP\_702 (Statistical Analysis Plan).

The reader of this SAP is encouraged to read the study protocol for details on the conduct of this study, the operational aspects of clinical assessments, and the timing for completing the participation of a patient in this study.

The SAP is intended to be in agreement with the protocol, especially with regard to the primary and all secondary endpoints and their respective analyses. However, the SAP may contain more details regarding these particular points of interest, or other types of analyses (eg, other endpoints). When differences exist in descriptions or explanations provided in the study protocol and this SAP, the SAP prevails; the differences will be explained in the clinical study report.

## 1. STUDY ENDPOINTS

### 1.1. Primary Efficacy Endpoints

The **primary efficacy endpoint** is the mean change from baseline (baseline period) in the monthly average number of headache days of at least moderate severity during the 12-week period after the first dose of the IMP.

### 1.2. Secondary Efficacy Endpoints

The secondary efficacy endpoints are:

- proportion of patients reaching at least 50% reduction from baseline (*baseline* period) in the monthly average number of headache days of at least moderate severity during the *12-week* period of treatment with the IMP
- proportion of patients reaching at least 50% reduction from baseline (baseline period) in the monthly average number of headache days of at least moderate severity during the first 4-week period after the first dose of the IMP
- proportion of patients reaching at least 50% reduction from baseline (baseline period) in the monthly average number of headache days of at least moderate severity during the 5- to 8-week period after the first dose of the IMP
- proportion of patients reaching at least 50% reduction from baseline (baseline period) in the monthly average number of headache days of at least moderate severity during the 9- to 12-week period after the first dose of the IMP
- mean change from baseline (*baseline* period) in the number of headache days of at least moderate severity during the first 4-week period after the first dose of the IMP
- mean change from baseline (*baseline* period) in the number of headache days of at least moderate severity during the 5- to 8-week period after the first dose of the IMP
- mean change from baseline (*baseline* period) in the number of headache days of at least moderate severity during the 9- to *12-week* period after the first dose of the IMP
- mean change from baseline (visit 2) in disability score, as measured by the 6-item Headache Impact Test (HIT-6) at week 12 after the first dose of the IMP
- mean change from baseline (visit 2) in the assessment of patient satisfaction, as measured by the Patient Global Impression of Change scale, at 4, 8, and 12 weeks after the first dose of the IMP

### 1.3. Safety Endpoints

The safety and tolerability endpoints are as follows:

- occurrence of adverse events during the study
- clinically significant changes in physical examinations, including body weight

Statistical Analysis Plan

- clinical laboratory (serum chemistry, hematology and coagulation, and urinalysis) test results at each visit
- vital signs (blood pressure, respiratory rate, body temperature, and pulse) measurements at each visit  
Note: Oxygen saturation and respiratory rate will be measured in cases of suspected anaphylaxis and severe hypersensitivity.
- 12-lead electrocardiogram (ECG) findings at each visit
- use of concomitant medication during the study
- number (%) of patients who did not complete the study (day 168, end of study)
- number (%) of patients who did not complete the study due to adverse events
- local tolerability at the injection site (ie, erythema, induration, ecchymosis, and pain) at the following time points postdose: day 0, day 28, and day 56
- hypersensitivity reaction assessment
- Columbia Suicide Severity Rating Scale (C-SSRS)

**1.4. Immunogenicity Assessment Endpoints**

The immunogenicity endpoints are antidrug antibodies (ADA) incidence and characteristics (eg, titer, kinetics, and neutralizing activities).

**1.5.**

[REDACTED]

- [REDACTED]
- [REDACTED]
- [REDACTED]
- [REDACTED]
- [REDACTED]
- [REDACTED]
- [REDACTED]

- [Redacted]
- | [Redacted]

- [REDACTED]
- [REDACTED]
- [REDACTED]
- [REDACTED]
- [REDACTED]
- [REDACTED]

## 1.6. Estimand for Primary Efficacy Endpoint

The primary estimand for this study is defined by the following 4 components:

1. **Target population:** male and female patients aged 18 to 70 years, inclusive, with a history of PTH (as defined by International Classification of Headache Disorders 3rd revision [ICHD-3] (beta version) criteria).
2. **Outcome measure:** mean change from baseline (baseline period) in the monthly average number of headache days of at least moderate severity during the 12 week period after the first dose of the IMP.
3. **Analysis set and handling of intercurrent events:** The full analysis set (FAS) will be used for efficacy analyses. FAS is a subset of the ITT analysis set including only patients who received at least 1 dose of IMP and had at least 1 post-baseline efficacy assessment on the primary endpoint. In the FAS, treatment will be assigned based on the treatment to which patients were randomized, regardless of which treatment they actually received.

For patients randomized to active treatment who did not complete the double-blind treatment period due to lack of efficacy, death, or adverse event, the average number of headache days in the remainder of the analysis window will be imputed as the mean monthly average of headache days in the same analysis window for patients assigned to placebo.

All other missing data for patients in either treatment group will be handled as follows:

- For patients who have  $\geq 10$  days of e-diary data in an analysis window, the monthly average number of headache days will be calculated based on data available in that analysis window and prorated to 28 days
- For patients who have  $< 10$  days of e-diary data in an analysis window, the monthly average number of headache days will be imputed using the mean monthly average of

headache days in the same analysis window for patients assigned to the same treatment group and having  $\geq 10$  days of e-diary data.

More details are provided in Section [6.1.4](#).

4. **Measure of treatment effect:** analysis of covariance model including treatment as fixed effect and the baseline number of headache days of at least moderate severity and the posttraumatic headache onset ( $< 12$  months and  $\geq 12$  months) as covariates.

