## 4.1. Patient Inclusion Criteria

Patients may be randomized/enrolled in this study only if they meet all of the following criteria:

- a. The patient is capable of giving signed informed consent as described in Appendix C, which includes compliance with the requirements and restrictions listed in the informed consent form (ICF) and in this protocol.
- b. The patient is a man or woman 18 to 70 years of age, inclusive.
- c. The patient has a body weight  $\geq$ 45 kg.
- d. Traumatic injury to the head has occurred, defined as a structural or functional injury resulting from the action of external forces. These include striking the head with or the head striking and object, penetration of the head by a foreign body, forces generated from blasts or explosions; or whiplash has occurred, defined as sudden and inadequately restrained acceleration/deceleration movements of the head with flexion/extension of the neck. Whiplash may occur after either high or low impact forces.
- e. The patient has a diagnosis of PTH as per the ICHD-3 (beta version) criteria:
  - Headache is reported to have developed within 7 days after one of the following:
    - o mild traumatic injury to the head
    - o regaining of consciousness following the injury to the head
    - o discontinuation of medication(s) that impair ability to sense or report headache following the injury to the head

In addition, the following criteria should be met:

- Headache persists for >1 month after injury to the head
- f. During the baseline period, the patient has at least 8 headache days of at least moderate severity, defined as a day when a patient reports at least 4 hours of headache (not necessarily consecutive) and at its worst at any point has at least moderate severity; or when a patient has a headache and takes a prescription abortive medication with intent to alleviate the headache (regardless of duration or severity).
- g. The patient demonstrated compliance with the electronic diary during the baseline period by entry of headache data at a minimum of 75% compliance.
- h. The patient is not using preventive medications for headache (presented in Appendix F) (ie, at least 5 half-lives have passed since last use) or is using them in

- a dose and regimen that have been stable for at least 2 months prior to beginning the baseline period.

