#### 6.1.4. Handling Missing E-diary Data

This section includes missing data handling for e-diary data. For other type of data, the missing data handling methods are provided in the analysis section for the endpoint if applicable.

**For analyses using ANCOVA or mixed model for repeated measures (MMRM)** based on monthly averages the missing data handling methods are as follows:

For patients randomized to active treatment group and did not completed the double-blind treatment period due to lack of efficacy, death, or adverse event, the number of headaches in an analysis window will be imputed as the following

$$\sum (\text{observed headaches during a analysis window}) + (N-X) * (\text{placebo average}/N)$$

Where

$N$  denotes the number of days in the analysis window, 84 days for 12-week analysis window and 28 days for 4-week analysis window;

$X (X > 0)$  denotes the number of days with e-diary within the analysis window;

“Placebo average” is the monthly average of number of headache during the analysis window from placebo patients who completed study.

For 12-week analysis window, the monthly average of the number of headaches will be prorated to 28 days using formula A;

All other missing data for patients in either treatment group will be handled as follows:

- For patients who have  $\geq 10$  days of e-diary data in an analysis window, the monthly average number of headache days will be calculated based on data available in that analysis window and prorated to 28 days using formula A;
- For patients who have  $< 10$  days of e-diary data in an analysis window, the monthly average number of headache days will be imputed using the mean monthly average of headache days in the same analysis window for patients assigned to the same treatment group and having  $\geq 10$  days of e-diary data.

**Note: the imputation is only for post-baseline data and applies to all efficacy endpoints related to the number of headache days.**

In addition, as a sensitivity analysis, the primary endpoint will be analyzed using a MMRM method. Detail is provided in Section 6.2.3.

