#### Example SAS code for ANCOVA

```
PROC MIXED DATA=<name>;
  CLASS TRTP ONSET;
  MODEL CHG= BASE ONSET TRTP /S;
  LSMEANS TRTP /DIFF=CONTROL ("Placebo") CL ALPHA=0.05;
  ODS OUTPUT LSMEANS= <name> DIFFS= <name> ;
RUN;
```

Where TRTP denotes the planned treatment group; CHG denotes the change from baseline in the monthly average number of headache days of at least moderate severity; BASE denotes the baseline monthly average number of headache days of at least moderate severity; ONSET denotes the posttraumatic headache onset (<12 months and  $\geq$ 12 months). In bold are the SAS key words.

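### The fill for fremanezumab failures uses the placebo group's raw headache-day level regardless of the patient's baseline; a baseline-predicted placebo value would be a cheap improvement

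*SAP*

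**What the plan says.** SAP 1.6 and Protocol 9.5.5.1 fill the rest of the analysis window after a fremanezumab patient stops for one of three reasons: the headache days "will be imputed as the mean monthly average of headache days in the same analysis window for patients assigned to placebo". SAP 6.1.4 names the patients concerned: "For patients randomized to active treatment group and did not completed the double-blind treatment period due to lack of efficacy, death, or adverse event". Their window total becomes observed headaches + (N - X) × (placebo average / N). X is the number of diary days, and N "denotes the number of days in the analysis window, 84 days for 12-week analysis window and 28 days for 4-week analysis window". The placebo average "is the monthly average of number of headache during the analysis window from placebo patients who completed study". Recorded diary days are kept and only missing days are filled. The patient's baseline does not enter.

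For other patients with fewer than 10 diary days in a window, "the monthly average number of headache days will be imputed using the mean monthly average of headache days in the same analysis window", taken from the patient's own treatment group. This too is a raw mean.

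The filled value enters the primary ANCOVA on change from baseline, "MODEL CHG= BASE ONSET TRTP /S". SAP 6.1.4 states that its rules cover both the ANCOVA and the MMRM.

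**The concern.** Baselines differ widely between patients. Entry requires that "the patient has at least 8 headache days of at least moderate severity", and values are prorated to 28 days, so 28 is the ceiling. The floor is only roughly 8, because the entry rule uses a different headache-day definition (duration or abortive medication) from the endpoint definition in Protocol 2.1.1.

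One fixed level is set against these different baselines. A failure with a high baseline is given a larger reduction than a placebo patient with that baseline would be expected to show. A failure with a low baseline is given a smaller reduction, or a worsening. If failures cluster at high baselines, the errors do not cancel and the primary difference moves toward fremanezumab. Only fremanezumab patients receive this fill, so no matching error arises in the placebo arm.

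**Working it through.** **Inputs from the documents.** Design difference 2.0 days and SD 4.4 (Protocol 16.1, new wording for Section 9.1). These reproduce the plan's sample size: noncentral-t power is 0.8003 at 77 per arm, and 77/0.9 = 85.6, so 86 per arm and 172 in total. Recruitment stopped at 87 (Protocol 3.2), so about 43 and 44 per arm. Windows are 84 and 28 days (SAP 6.1.4).

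**Assumed inputs, not in the documents.** Placebo level P = 12 days per 28 (range 8 to 16); mean baseline 16; slope of on-study level on baseline b = 0.7 (range 0.5 to 0.9); and the number of failures, their stopping day and their baseline excess over the mean.

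**Step 1: one patient.** Baseline 24, no improvement, stops after 28 diary days. Missing days are filled at the rate P/28, which is the sense of SAP 1.6.

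- Raw fill: (24 + 12 + 12)/3 = 16.0, change -8.0.
- Predicted placebo level at baseline 24: 12 + 0.7 × (24 - 16) = 17.6. Score (24 + 17.6 + 17.6)/3 = 19.7, change -4.3.
- Gap: (56/84) × 0.7 × 8 = 3.7 days. P cancels from the gap.
- With b = 0.5 the predicted level is 16.0 and the change -5.3; with b = 0.9 they are 19.2 and -3.2.
- With P from 8 to 16 the raw-fill change runs from -10.7 to -5.3.
- If the patient stops at day 56 instead, the gap halves to (28/84) × 0.7 × 8 = 1.9.

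A low baseline errs the other way. At baseline 10 the raw fill gives (10 + 12 + 12)/3 = 11.3, change +1.3. The predicted level is 12 + 0.7 × (10 - 16) = 7.8, which gives (10 + 7.8 + 7.8)/3 = 8.5, change -1.5.

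**Step 2: does the baseline covariate remove it?** At baseline 24 the fitted placebo change is 17.6 - 24 = -6.4. The raw-fill score of -8.0 is 1.6 days better than that; the predicted-fill score of -4.3 is 2.1 days worse. The covariate absorbs most of the -8.0 but leaves the 3.7-day gap. The filled part of the change falls one-for-one with baseline, while the fitted slope comes mainly from patients with observed data.

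**Step 3: the treatment difference.** Averaging the gap over the fremanezumab arm gives

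shift ≈ -(failures/43) × ((84 - X)/84) × b × (baseline excess of failures).

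With an assumed excess of 4 days:

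| Failures | Stop day | b | Shift (days) |
|---|---|---|---|
| 2 of 43 | 56 | 0.5 | -0.03 |
| 2 of 43 | 56 | 0.7 | -0.04 |
| 4 of 43 | 28 | 0.7 | -0.17 |
| 6 of 43 | 28 | 0.7 | -0.26 |

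Simulation agrees. At b = 0.7 with failures likelier at high baseline, the shift was -0.17 (10% failures) and -0.25 (15%) for day-28 stops, and -0.045 for 2 of 43 stopping at day 56. Over slopes 0.5 to 0.9 the shift ran from about -0.03 to about -0.3. The predicted fill stayed within 0.01 of the placebo-like truth. With failures unrelated to baseline the raw-fill shift was about zero.

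**Step 4: the obvious shortcut.** Own baseline plus the placebo mean change equals the predicted value only at b = 1. Its error is +(failures/43) × ((84 - X)/84) × (1 - b) × excess. For 4 of 43, day 28, excess 4 and b = 0.7 this is +0.07 (simulated +0.08). At b = 0.5 it is +0.12, as large as the raw fill's -0.12.

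**Step 5: the MMRM.** SAP 6.2.3 sets no missing-data rule of its own, so 6.1.4 governs. Its failure formula is defined for X > 0. A month with no diary days is filled either under SAP 1.6 or under the fewer-than-10-days rule. Both insert a group mean with no baseline term.

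**A separate matter.** Read literally, 6.1.4 divides a 28-day placebo average by 84 in the primary window. The same patient then gets 24 + 56 × 12/84 = 32 days over 84, or 10.7 per 28 days, a change of -13.3. SAP 1.6 and 6.1.4 also differ on whether the reference group is all placebo patients or placebo completers. Correcting either leaves the present point in place.

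**The case against.** The strongest reply is that the placebo group mean is prespecified in both documents. No passage says that the estimand means the outcome of a placebo patient with the same baseline; that is an inference from an outcome and model that both use baseline. This stands, and it is why the point is an improvement rather than an error against the plan's own text.

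The net shift also needs several assumptions. Failures must have above-average baselines, and the documents do not say so. The rule covers death and adverse events as well as lack of efficacy, and a high-baseline tilt is not obvious for those. Failure rates of 10 to 15% for these three reasons are generous beside a planning figure of 10% discontinuation for any reason. Recorded days are retained, so later stops shrink the shift. All of this stands and pulls toward the lower end of the range.

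A reader might infer from -8.0 that a failure is counted as a large improver, at four times the 2.0-day design effect. The documents do not support that. It sets one patient's change against a between-group difference, and the primary model conditions on baseline, so the patient sits only 1.6 days better than fitted (Step 2). A reader might also compare -8.0 with own baseline plus the assumed placebo mean change of -4, which scores (24 + 20 + 20)/3 = 21.3, change -2.7. That comparison assumes slope 1, and the documents give no slope.

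What the reply does not remove is that the fill ignores a covariate on which the analysis conditions, and that the planned sensitivity analysis would not reveal the effect.

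**Conclusion.** The point holds as a modest, cheap improvement. For a single high-baseline failure the raw fill differs from a baseline-predicted placebo value by several days (3.7 in the example). For the primary treatment difference the shift is roughly 0.05 to 0.25 days toward fremanezumab at slope 0.7, and about 0.03 to 0.3 over slopes 0.5 to 0.9, depending on how many patients fail and when. The range at slope 0.7 is 2.5% to 12.5% of the 2.0-day design difference. Against a standard error of 4.4 × √(1/43 + 1/44) = 0.94 it is about 0.05 to 0.27 standard errors.

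These sizes rest on assumed values for the mean baseline, the slope, and the number, timing and baseline excess of failures. A reader might infer that the primary result is biased in favour of fremanezumab. The documents do not establish that: the shift is about zero if failures are unrelated to baseline, and it would reverse if failures had below-average baselines.

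**What to change.** Before unblinding, in SAP 1.6 and 6.1.4 and Protocol 9.5.5.1 (with the matching synopsis text), replace the raw placebo mean by the placebo-arm value for that window, predicted from the patient's own baseline and PTH-onset stratum. Reference-based multiple imputation with the same covariates is an alternative. Do not use own baseline plus placebo mean change, which is unbiased only if the slope is 1. If only the SAP is changed, record the difference in SAP Section 17, which now lists none.

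A within-arm predicted value for windows with fewer than 10 diary days is an optional change for consistency. It matters mainly for the monthly windows, since few patients would have under 10 diary days in 84.

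The cost is a sentence in each place and a little more programming. The downside is that low-baseline failures receive a more favourable value than under the raw fill.
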